Trial rationale	
Diabetic macular ischemia (DMI) is a complication of diabetic retinopathy (DR) and can lead to vision loss. Currently, there are no approved or effective treatments to prevent either onset or progression of DMI in DR patients.
 
As a transition from preclinical investigations to clinical development in this first-in human trial, the safety, tolerability, pharmacokinetics and early biological response of BI 765128 will be investigated in volunteer subjects with DMI.
 
This trial will include subjects affected by DMI with visual loss since intravitreal injections in subjects without the condition would not be considered ethically justifiable.

Trial objective(s)	The objective of this trial is to determine the safety and tolerability of BI 765128 in panretinal photocoagulation (PRP) treated diabetic retinopathy (DR) patients with diabetic macular ischemia (DMI), based on the primary endpoint, the occurrence of dose limiting events (DLE) (see Section 5.2.1) in the 7 days post administration (Part A) or the occurrence of drug-related AEs until EOS (Part B). The safety, tolerability and early biological response after multiple IVT injections of BI 765128 will also be investigated.

Trial endpoints	
Primary endpoints:
 
Part A:
 
 • Number of subjects with ocular dose limiting events (DLEs) from drug administration until day 8 (7 days after treatment) 
Part B:
 
 • Number of subjects with drug-related AEs from drug administration until EOS 
Secondary endpoints:
 
Part A:
 
 • Number of subjects with drug related AEs at EOS • Number of subjects with any ocular AEs (eye disorders) at EOS 
Part B:
 
 • Change from baseline of the size of the FAZ in optical coherence tomography angiography (OCTA) at visit 5 • Change from baseline of the size of the FAZ in optical coherence tomography angiography (OCTA) at visit 6 • Change from baseline of the size of the FAZ in optical coherence tomography angiography (OCTA) at visit 7 • Change from baseline of BCVA at Visit 7 • Number of subjects with any ocular AEs (eye disorders) from drug administration until EOS
Trial design	
This trial will consist of two parts, A and B. Part A will be non-randomized, open-label and uncontrolled. Part B will be double-masked, randomized and sham-controlled (ratio 2:1).

Total number of subjects entered	
Approximately 48 subjects in total

Number of subjects on each treatment	
Up to 18 subjects in Part A (depending on the dose escalation) and 30 subjects in Part B. In Part B subjects will be randomized to receive either IVT injection or sham injection.

Diagnosis	
Diabetic macular ischemia (DMI) in patients previously treated with Panretinal photocoagulation (PRP) for diabetic retinopathy (DR)

Main in- and exclusion criteria	
Main inclusion criteria:
 
Part A:
 
 • Panretinal photocoagulation-treated DR patients with either no or inactive retinal neovascularization per investigator judgement in the study eye • Evidence of DMI per investigator's judgement, defined as any degree of disruption of retinal vascularity in superficial and/or deep retinal plexus in OCTA • Best-corrected VA \leq75 letters (20/32) in the study eye

	
Part B:
 
 • Panretinal photocoagulation-treated DR patients with either no or inactive retinal neovascularization per investigator judgement • Presence of significant DMI: Large foveal avascular zone (FAZ) defined as those with $\geq 0.5\text{mm}^2$ area present on OCTA. If FAZ is $< 0.5\text{mm}^2$ then an enlarged peri-foveal inter-capillary space in at least 1 quadrant will be sufficient. • Best-corrected VA ≤ 85 letters (20/20) in the study eye 
Main exclusion criteria:
 
Part A:
 
 • Patients receiving IVT injections for active Diabetic Macular Edema (DME) (anti-VEGF, steroids) and macular laser in the previous 3 months to screening in the study eye • Subjects receiving anti-VEGF IVT injections for active DR in the previous 3 months to screening in the study eye 
Part B:
 
 • Diabetic Macular Edema (DME), defined as a CST $\geq 305\mu\text{m}$ for men and $\geq 290\mu\text{m}$ for women (Optovue Angiovue) in the study eye • Subjects receiving IVT injections for active DME (anti-VEGF, steroids) and macular laser in the previous 3 months to screening in the study eye • History of vitrectomy in the study eye
Test product(s)	BI 765128, solution for injection
dose	
Part A: [REDACTED] mg (single doses)
 
Part B: The highest dose ([REDACTED] mg) [REDACTED] if established as safe and tolerable during Part A

mode of administration	Intravitreal injection
Comparator product(s)	Not applicable
dose	Not applicable
mode of administration	Not applicable
Duration of treatment	
Part A: single intravitreal dose
 
Part B: 3 intravitreal doses at [REDACTED] [REDACTED]

Statistical methods	The main objectives of this trial will be assessed by calculating descriptive statistics on DLEs and drug related AEs. For the Part B these will be compared descriptively between the treatment groups.

	The dose escalation in the SRD part will be guided by a Bayesian logistic regression model (BLRM) with overdose control that will be fitted to binary toxicity outcomes. The estimates of parameters will be updated as data are accumulated using the BLRM.
--	--

FLOW CHART I (PART A)

Trial Periods	Screening Period	Treatment Visit	Follow-up period					End of study
			3	4	5	6	7	
Visit	1	2	3	4	5	6	7	8
Study Days	Duration 3 to 28 days	Day 1	4	8	15	29	57	99
Study Weeks				Week 1	Week 2	Week 4	Week 8	Week 14
Time window for visits (days)		none	±1	±2	±2	±3	±7	±7
Informed consent	X							
Demographics	X							
Medical history	X							
Physical examination (including weight)	X	X ⁽¹⁾				X	X	X
Vital signs	X	X	X	X	X	X	X	X
Laboratory tests	X	X		X	X	X	X	X
12-lead ECG ⁽²⁾	X	X	X			X	X	X
Review of in-/exclusion criteria	X	X						
Dose Assignment		X						
IVT drug administration		X						
Pregnancy test ⁽³⁾	X _S	X _S		X _U	X _U	X _U	X _U	X _U
PK 								
 sampling ⁽⁴⁾		X			X	X	X	X
BCVA testing	X	X	X	X	X	X	X	X
SD-OCT	X	X	X	X	X	X	X	X
OCT Angiography	X	X	X	X	X	X	X	X
Fundus Photo	X	X		X	X	X	X	X
Slit lamp and intra-ocular pressure (IOP)	X	X	X	X	X	X	X	X
All AEs/SAEs/AESIs	X	X	X	X	X	X	X	X
Concomitant therapy	X	X	X	X	X	X	X	X
Completion of subject participation ⁽⁵⁾								X

(1) Could be repeated as deemed necessary at investigator's discretion.

(2) Single ECGs are to be recorded shortly before the PK sampling at the respective time points, (Section 5.2.5. and Appendix 10.1).

Proprietary confidential information © 2023 Boehringer Ingelheim International GmbH or one or more of its affiliated companies

- (³) Pregnancy testing: serum pregnancy test (X_S) is done at screening and on day 1 if more than a week elapsed between screening and day 1, and at the other visits as a reflex when urine testing (X_U) is positive.
- (⁴) 
- (⁵) Completion of subject participation also needs to be completed in the eCRF if the subject withdraws prematurely following assignment to dose level (Section [3.3.4](#))

FLOW CHART II (PART B)

Trial Periods	Screening Period	Treatment Period			Follow-up Period		End of Study
		2	3	4	5	6	
Visit	1 ⁽¹⁾	2	3	4	5	6	7
Study Day/ Week	Duration 3 to 28 days	1			85 Week 12	113 Week 16	141 Week 20
Time window for visits (days)		none	±3	±3	±7	±7	±7
Informed consent	X						
Informed consent Aqueous sampling (optional)	X						
Demographics	X						
Medical history	X						
Physical examination (including weight)	X				X		
Vital signs	X	X	X	X	X	X	X
Laboratory tests	X	X	X	X	X	X	X
12-lead ECG ⁽²⁾	X	X	X	X	X		
Review of in-/exclusion criteria	X	X					
Dose Assignment		X					
Randomization		X					
[REDACTED]		■	■	■			
Pregnancy test ⁽³⁾	Xs	Xs	Xu	Xu	Xu	Xu	Xu
[REDACTED] ⁽⁴⁾		X	X	X	X	X	X
PK [REDACTED]		■	■	■	■	■	■
[REDACTED]		X		X		X	X
BCVA testing	X	X	X	X	X	X	X
SD-OCT	X	X	X	X	X	X	X
OCT Angiography	X	X	X	X	X	X	X
Fundus Photo	X	X	X	X	X	X	X
Slit lamp and intra-ocular pressure (IOP)	X	X	X	X	X	X	X
[REDACTED]		X	X	X	X	X	X
All AEs/SAEs/AESIs	X	X	X	X	X	X	X

Trial Periods	Screening Period	Treatment Period			Follow-up Period		End of Study
Concomitant therapy	X	X	X	X	X	X	X
Completion of subject participation ⁽⁶⁾							X

- (1) Screening visit should be performed in two visits. After Informed consent is obtained, visual acuity testing, SD-OCT, OCT Angiography and fundus photography should be performed and sent to central reading service. If subject is eligible based on the results from the reading centre, the subject should return to complete the rest of the screening. In case of scheduling difficulty for certain subjects, screening can be performed in one visit.
- (2) Single ECGs are to be recorded shortly before the PK sampling at the respective time points: (Section [5.2.5](#) and [Appendix 10.1](#)).
- (3) Pregnancy testing: serum pregnancy test (Xs) is done at screening and on day 1 if more than a week elapsed between screening and day 1, and at the other visits as a reflex when urine testing (Xu) is positive.
- (4) 
- (5) See separate flow chart for Aqueous sampling (Table [10.1:3](#)). Aqueous samples are collected immediately before drug administration at Visits 2 and 4. At visits 6 and 7, when no drug is administered, the aqueous samples can be collected at any time during the visit (Section [4.1.5](#))
- (6) Completion of subject participation also needs to be completed in the eCRF if the subject withdraws prematurely following assignment to dose level (Section [3.3.4](#)).

TABLE OF CONTENTS

TITLE PAGE	1
CLINICAL TRIAL PROTOCOL SYNOPSIS	2
FLOW CHART I (PART A).....	6
FLOW CHART II (PART B).....	8
TABLE OF CONTENTS	10
ABBREVIATIONS	14

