Risks related to IVT injection	Clinical trials assessing efficacy and safety in marketed drugs administered via IVT injection showed a low rate of complications associated with IVT injection procedure. Because the procedure of intravitreal injection of BI 765128 is the same (use of a filter needle to extract product from the vial and same needle size for injection, 30 gauge), the expected adverse events related to the procedure are considered equal to what was observed with marketed drugs.	At each visit a complete ophthalmic examination will be performed to detect early signs of complications. Intra-ocular pressure (IOP) will be measured at each visit.
Risks related to blood sampling	Blood sampling may be accompanied by mild bruising and also in rare cases, by transient inflammation of the wall of the vein. In addition, in rare cases a nerve might be injured while inserting the venous catheter, potentially resulting in paraesthesia, reduced sensibility, and/or pain for an indefinite period.	The total volume of blood withdrawn during the entire study per subject will not exceed the volume of appr. 500 mL.
Risks related to Anterior Chamber tap	Corneal abrasion, cataract formation, infection, iris and lens trauma	Only experienced physicians will undertake the procedure

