4.1.5 Intravitreal Injection Technique and Sham Injection

IVT injections must be carried out according to medical standards and applicable guidelines by a qualified physician experienced in administering IVT injections. In general, adequate anaesthesia and asepsis, including topical broad-spectrum microbicide (e.g. povidone iodine applied to the periocular skin, eyelid and ocular surface) have to be ensured. Surgical hand disinfection, sterile gloves, a sterile drape, and a sterile eyelid speculum (or equivalent) to be used in accordance with local standards and regulations.

Part B is designed double-masked and personnel of the trial site are masked. Therefore, in Part B, an unmasked injector with no other involvement in the trial will administer IVT/sham injections.

For a sham injection, all pre- and post-injection procedures are identical compared to IVT injections. For a sham injection, the hub of a syringe without a needle is pressed against the conjunctival surface to simulate the force of an actual injection. For sham aqueous sampling, all procedures are identical to aqueous sampling, the hub of a syringe without a needle is pressed gently against the corneal surface to simulate aqueous sampling.

Use of antibiotics in the pre-, peri-, or post-injection period is at investigator's discretion.

After administration of BI 765128, subjects will be monitored according to standard local practice. In this minimum post-dose observation period, systemic and ocular conditions will be monitored according to local practice for such procedures.

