6.2 DETAILS OF TRIAL PROCEDURES AT SELECTED VISITS

Study procedures and assessments to be performed at each visit are listed in the Flow Chart I, Flow Chart II, and in the appendix 10.1. Additional details regarding visit procedures are provided below.

All ophthalmic examinations will be performed in both eyes and should be performed in the specific order described below:

- Before pupil dilation: BCVA assessment and [REDACTED] assessment
- After dilation: slit lamp examination, SD-OCT, OCTA, colour fundus photography.
- At the end: ocular tonometry (for determination of IOP)

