6.2.2 Treatment period(s)

For Part A, masking is not required for the IVT injection preparation or administration. For Part B, IVT injection will be prepared by the unmasked pharmacist/qualified person (Section 4.1.6). In addition, an unmasked injector (Section 4.1.6) with no other involvement in the trial will administer either active or sham injection according to the treatment assigned by IRT. IVT injections must be carried out according to medical standards and applicable guidelines by a qualified physician experienced in administering IVT injections and will be done as part of drug administration visit procedures (Visit 2 for Part A and Visits 2, 3 and 4 for Part B) after the other ophthalmologic assessments in the [Flow Chart I](#) and [Flow Chart II](#) have been performed (please see Section 4.1 for details).

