10. APPENDICES

10.1

[figure not shown]

Table 10.1: 3 Time schedule for optional [REDACTED] (Part B)

Trial Periods	Visit	Day	Time Point	Optional [REDACTED]
Treatment	2	1	Just before drug administration	X*
	3	29 (±3)		
	4	57 (±3)	Just before drug administration	X*
Follow-up	5	85 (±7)		
Follow-up	6	113 (±7)	Any time during the visit	X*
EOS	7	141 (±7)	Any time during the visit	X*

* Optional [REDACTED] samples are collected immediately before drug administration at Visits 2 and 4. At visits 6 and 7, when no drug is administered, the aqueous samples can be collected at any time during the visit.

**10.2 BENEFIT-RISK ASSESSMENT IN CONTEXT OF COVID-19
PANDEMIC FOR SUBJECTS PARTICIPATING IN TRIAL 1451-0001
INVESTIGATING BI 765128**

STUDY POPULATION

As per the Centers for Disease Control and prevention (CDC), people with serious chronic medical conditions, including diabetes and heart disease, might be at higher risk for severe illness from COVID-19.

BENEFITS AND RISKS CONCLUSIONS AND RECOMMENDATIONS

Currently, there is no evidence that based on the pharmacological mechanism and existing non-clinical data BI 765128 either may affect the immune system or increase the risk of progression of COVID-19 infection. BI 765128 is administered intravitreally using standard aseptic technique.

The low dosage of BI 765128 means the systemic exposure is expected to be very low.

Therefore, no change on the Benefit-Risk assessment of the compound in the context of the COVID-19 pandemic is foreseen.

The current study population is potentially at higher risk of COVID-19 infection due to background or concomitant diseases. Enrollment will start when the local situation allows, and appropriate risk mitigation measures (e.g. use of Personal Protective Equipment) will be implemented in line with local instructions and recommendations

The investigators will take the totality of information related to each single subject and the local COVID-19 situation into consideration when performing the individual benefit-risk assessment on a case-by-case basis. Considering all aspects, the investigator will decide upon each subject's (continued) participation in the trial. BI as the sponsor, where required, will support the investigator in their decision finding. It is acknowledged that the investigator may decide to implement protocol deviations where this protects the safety, wellbeing and/or is in the best interest of the subject.

DETAILS OF TRIAL PROCEDURES AT SELECTED VISITS

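### Optional aqueous sampling at Visits 6 and 7 has no fixed place in the examination order, so a real or sham tap can precede the FAZ and BCVA endpoint readings

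*Protocol*

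**What the plan says.** Flow Chart II, footnote 5, sets two timing rules for the optional aqueous sample. For the dosing visits: "Aqueous samples are collected immediately before drug administration at Visits 2 and 4". For the follow-up visits: "At visits 6 and 7, when no drug is administered, the aqueous samples can be collected at any time during the visit". Table 10.1: 3 enters "Any time during the visit" as the time point for both Visit 6 (day 113) and Visit 7 (day 141).

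Protocol Section 6.2 says of the eye examinations: "All ophthalmic examinations will be performed in both eyes and should be performed in the specific order described below". The order is BCVA before dilation; then slit lamp, SD-OCT, OCTA and fundus photography; then tonometry at the end. Aqueous sampling is not in the list. Section 6.2.2 places the injection after the other eye assessments, but it covers drug administration visits only (Visits 2, 3 and 4 in Part B).

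Footnote 5 refers to Section 4.1.5, which gives no timing rule. It describes the sham version of the sampling: "the hub of a syringe without a needle is pressed gently against the corneal surface to simulate aqueous sampling". For the real tap, Table 1.4.2.6: 1 lists these risks: "Corneal abrasion, cataract formation, infection, iris and lens trauma".

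**The concern.** The permission is explicit. A site that follows the protocol to the letter may sample before any or all of the eye assessments at the last two visits. The real procedure enters the anterior chamber and the sham does not, so a disturbance from the puncture would fall on one kind of subject only. By the natural reading of Section 4.1.5 the active arm has the real tap and the sham arm the hub press, though no sentence assigns them by arm.

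Two things are at stake. One is the comparison of change from baseline: Visits 6 and 7 are two of the three FAZ secondary endpoint visits, Visit 7 is the only BCVA one, and the fast track analysis of FAZ is run once the last subject has attended Visit 6 (SAP Section 7.5.3). The other is masking. BCVA, slit lamp and IOP are measured at the site by staff who should stay masked, and a slit-lamp examination after a tap might show whether the cornea was entered. The Part B primary endpoint, drug-related AEs, depends on a causality judgement made at the site.

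**Working it through.** The plan states no figure on this point, so there is none to reproduce. The check sets the timing rules side by side.

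| Visit | Aqueous sampling | Order against the eye assessments | Secondary endpoint role |
|---|---|---|---|
| 2 | Yes | Just before the injection, which follows the assessments (6.2.2) | Baseline for FAZ and BCVA (5.1) |
| 4 | Yes | As at Visit 2 | None |
| 5 | No | Not applicable | FAZ |
| 6 | Yes | Open | FAZ |
| 7 | Yes | Open | FAZ and BCVA |

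1. *Baseline.* Footnote 5 and Section 6.2.2 together imply that the Visit 2 readings come before the tap.
2. *Endpoint visits.* No drug is given at Visits 6 and 7, so Section 6.2.2 does not apply. Section 6.2 is silent on sampling and footnote 5 removes any limit. Readings may come before or after the tap.
3. *Change from baseline.* A reading taken after the tap is compared with one taken before it. Visit 5 has no sampling and is not exposed to a same-visit tap.
4. *Analysis.* The MMRM in SAP Section 7.5.2 has terms for treatment, visit, baseline and their interactions with visit, and none for sampling. The intercurrent events in SAP Section 6.3 do not include a tap. The SAP text available therefore neither adjusts for nor excludes an affected reading.
5. *Who samples.* Table 4.1.6.1:1 gives the unmasked injector the active and sham injections only. Table 1.4.2.6: 1 limits the tap to experienced physicians. No unmasked role is named for it.

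Ignoring covariate adjustment, the bias in the arm difference at one visit is

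bias = p(active) × d(tap) − p(sham) × d(hub),

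where p is the share of the arm sampled before the assessment in question and d is the mean shift that the procedure causes in that reading. The documents give none of the four quantities, so the bias cannot be computed.

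Two facts from the documents set the scale. With 20 active and 10 sham subjects, one affected reading moves its arm mean by 1/20 = 5% of that subject's shift in the active arm and by 1/10 = 10% in the sham arm. For FAZ, Section 7.6 equates 6% with 0.0462 mm², so 1% is 0.0462/6 = 0.0077 mm² and the assumed 10% effect is 0.077 mm². Any bias in FAZ would have to be judged against that amount.

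**The case against.** The case on the other side is substantial, and much of it limits the point.

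- *Sampling first is permitted, not planned.* A reader might infer that the Visit 6 and 7 readings are biased, or that every sampled subject is affected. The documents do not support either. Only subjects in the optional subset whose site samples before a given assessment are exposed.
- *No effect of a tap is documented.* The listed risks are complications, not a routine same-day loss of vision or change in FAZ. Putting a number of letters on the shift would have no source in the documents. Apart from the hub press, the sham sampling procedures match the real ones, so effects of preparation and corneal contact could occur in both arms.
- *FAZ grading is protected.* OCTA images are graded by an independent reading centre (protocol Section 5.1). A reader might infer that examiner unmasking reaches the FAZ grading, but the exposure there is limited to image acquisition. BCVA, slit lamp and IOP are more directly exposed.
- *The reach into the primary endpoint is short.* A clue at Visit 6 comes at day 113, and routine AE collection ends at Visit 7. No text says that a puncture can be recognised at the slit lamp.
- *The Laboratory Manual may set an order.* Section 5.4 says that it holds the full collection instructions, and it is not among the documents. If it does set one, the protocol's open wording still needs to be brought into line.
- *Sampling last means no scheduled examination after the tap*, and Visit 7 is the final visit. This is a real cost. It is partly answered by Visits 2 and 4, where the tap already follows the eye assessments. The parallel is incomplete, because the monitoring in Section 4.1.5 is tied to administration of BI 765128, which does not occur at Visits 6 and 7.

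What stands is that the timing is expressly open at two endpoint visits and implicitly fixed at baseline.

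**Conclusion.** The point holds as an ordering gap that can bias change from baseline differently by arm at Visits 6 and 7 and may give a masked site examiner a clue to treatment. It does not show that bias or unmasking will occur.

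The size is unknown, for the reasons given with the formula. The conclusion rests on two assumptions: that the real tap and the hub press go to the active and sham arms respectively, and that no document outside the protocol and SAP already fixes the order. Part B is exploratory, with no confirmatory testing, and only an optional subset is involved. This is a cheap improvement, not a threat to the trial.

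**What to change.** In Flow Chart II footnote 5, Table 10.1: 3 and Section 6.2, state that at Visits 6 and 7 real or sham aqueous sampling takes place after that visit's endpoint ophthalmic assessments, including the scheduled tonometry, are complete. Align the Laboratory Manual. Preferably, name someone not involved in masked assessments to do the sampling, such as the existing unmasked injector. While editing, add a sentence to Section 4.1.5 saying which arm receives the sham version.

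The cost is a few sentences and no extra visit or procedure. The downsides are less scheduling freedom at two visits, the injector's attendance where sampling occurs, and no scheduled examination after the tap. Whether a post-procedure safety check is needed is for the sponsor to decide; its results should be kept separate from the endpoint readings.
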